#### **7.12.6.2 The time (days) to repeat injection of SP-102**

The time to repeat injection of SP-102 will be analyzed using survival analysis methods. Subjects that do not receive a repeat injection will be censored at 20 weeks, and subjects who discontinue the study prior to 20 weeks without receiving a repeat injection will be censored at the time of discontinuation. The Kaplan-Meier estimator will be used to estimate the quartiles of the time to repeat injection in days. A Cox proportional hazards model will be utilized to test the treatment difference in time to repeat injection while adjusting for site, and Pain Catastrophizing Scale. The response variable of the Cox model will be time to repeat injection. The treatment group categories for this analysis will be the SP-102 and placebo groups. The quartiles and their corresponding 95% CIs from the Kaplan-Meier estimation, and the hazard ratio of SP-102 to placebo with its 95% CI and p-value will be presented. A survival plot of time to repeat injection will also be presented. Listings of time to repeat injection will be presented.

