## 2 INTRODUCTION

This document details the planned statistical analyses for the Scilex Pharmaceuticals, Inc., protocol “SP-102-02” study titled “Corticosteroid Lumbar Epidural Analgesia for Radiculopathy (C.L.E.A.R.)”. Scilex Pharmaceuticals, Inc. is the new name of Semnur Pharmaceuticals, Inc. Previous study documents include “Semnur”; however, due to the merger, this document and any other documents that are yet to be finalized, approved, and signed will include “Scilex”.

The proposed analyses are based on the contents of the final version (Version 4.0) of the protocol (dated 24-MAY-2018).

This is a double-blind (DB), randomized, placebo-controlled, multicenter study in subjects with lumbosacral radicular pain evaluating the safety and efficacy of a single SP-102 injection administered transforaminally (TF) compared to a single placebo injection administered intramuscularly (IM), followed by an open-label (OL) safety extension, evaluating an optional repeat SP-102 TF injection, if indicated, administered 4 to 20 weeks later. Subjects will be followed for 24 weeks following the initial treatment (“index injection”).

Eligible subjects will be randomly assigned (in a 1:1 ratio) on Day (D) 1 to receive a single dose of an SP-102 TF or placebo injection [REDACTED]

[REDACTED] This first injection is referred to as the “index injection”. An appropriately trained physician, hereafter called the Injection Physician, administering the double-blind investigational product (IPr) and other assisting staff (eg, nurse) will, therefore, not be blinded to the treatment assignment, while the rest of study staff involved in assessments and collection of data will remain blinded. Procedures will be in place at each site to ensure blinding, minimizing personnel involved with injection, and guarantee sequestration of imaging data acquired at the time of injection.

Each subject will have the option of receiving 1 supplemental OL TF injection of SP-102 (“repeat injection”). To qualify for the repeat injection, subjects must meet Repeat Injection Inclusion Criteria, Numeric Pain Rating Scale (NPRS) average pain score in the affected leg, and investigator judgment. The repeat injection may be administered between Weeks 4 and 20. Eligible subjects will receive OL SP-102 repeat injection regardless of their initial treatment assignment (SP-102 or placebo).

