### 7.1 Analysis and Reporting Periods

Baseline, efficacy, and safety data will be summarized for the following analysis periods:

- Primary analysis period which includes data from baseline through 4 weeks of treatment
- Secondary analysis period which includes data from baseline to end of study (Week 24)

Also, there are two reporting periods in this study in which for each reporting period, data are summarized for both the primary and secondary analysis periods. These reporting periods are as follows:

- Primary analysis:

This is the final inferential analysis of all efficacy endpoints, along with analysis of the safety endpoints up to Week12, which will be performed after all subjects complete the 12-week assessments and all data are cleaned.

[REDACTED]

[REDACTED] For data that are collected on an ongoing basis throughout the study (eg adverse events, concomitant medications), the subject's actual Week 12 visit date will be used as a cutoff for the data in the primary analysis. For subjects who did not complete Week 12 and withdrew early, the cutoff for the data would be the earliest of the subject's projected Day 85 and discontinuation date.

- Full analysis:  
After the subjects in the OL safety extension portion of the study complete the study up to Week 24, the database will be locked, and the corresponding analysis tables produced for the primary analysis will be updated with the descriptive statistics of the Week 16, Week 20, and Week 24 data added.

Thus, exactly the same set of outputs will be produced for the primary analysis and full analysis.

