#### **7.12.6.3 Proportion of subjects receiving repeat injection.**

The proportion of subjects receiving repeat injections will be compared between the two treatment groups using a Chi-Square test. The proportion of subjects receiving a repeat injection will be summarized by treatment group.

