### 13 LIST OF TABLES, FIGURES AND LISTINGS

The following table includes details of the tables, figures and listings to be included within each section of the eCTD. The eCTD section is shown in bold. The following validation methods maybe used

- Independent programming of numbers and manual review of format (IP)
- Independent programming by statistician of numbers and manual review of format (Stat IP)
- Manual review (MR)
- Code review (CR)

These sets of outputs will be produced twice:

- one for the primary analysis (which will occur after all subjects complete the 12-week assessments) AND
- another for the full analysis (which will occur after the subjects in the OL safety extension portion of the study complete the study up to Week 24)

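### At the Week 12 read, the 20-week censoring rule for time to repeat injection credits follow-up not yet observed, and the proportion repeated has no stated window (minor).

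*SAP*

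**What the plan says.** - **Status of the Week 12 read.** SAP 7.1 says of the analysis after all subjects complete Week 12: "This is the final inferential analysis of all efficacy endpoints". For data collected on an ongoing basis it cuts at each subject's actual Week 12 visit. Adverse events and concomitant medications are given as examples; repeat-injection dates are not named.
- **The later read.** At the full analysis the tables "will be updated with the descriptive statistics of the Week 16, Week 20, and Week 24 data added". The same section adds that "exactly the same set of outputs will be produced for the primary analysis and full analysis", and SAP 13 repeats the point: "These sets of outputs will be produced twice".
- **Time to repeat injection (SAP 7.12.6.2).** "Subjects that do not receive a repeat injection will be censored at 20 weeks"; those who discontinue earlier are censored at discontinuation. From the Cox model, "the hazard ratio of SP-102 to placebo with its 95% CI and p-value will be presented", together with a survival plot.
- **Proportion repeated (SAP 7.12.6.3).** "The proportion of subjects receiving repeat injections will be compared between the two treatment groups using a Chi-Square test". No time point or window is given.
- **When a repeat can occur (SAP 2).** "The repeat injection may be administered between Weeks 4 and 20".
- **General rule (SAP 7.3.3).** In every time-to-event analysis, subjects without the event are censored when last known to be event-free.
- **Comparable endpoints.** Cumulative rescue use, time to first rescue dose and the proportion using rescue (SAP 7.12.6.13 to 7.12.6.15) all have 4-week and 12-week horizons; the first two name Day 29 and Day 85.

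**The concern.** The inferential read is placed at Week 12, while the censoring time for one of its endpoints is eight weeks later. A subject seen event-free to Day 85 and still in the study would be entered as event-free to Day 141. The survival plot in the first report would then imply follow-up that it did not use.

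The two repeat-injection endpoints also lack what the rescue endpoints have: a stated horizon for the read at which they are tested. Both are other secondary endpoints in the fixed sequence of SAP 7.12.6.19, so the data behind each test should be beyond doubt. The ordered list is redacted. SAP 11 says PGIC moved from 13th to third. Counting the primary as first, the list in Protocol 5.2.8.3 does put PGIC 13th, and moving it up would leave these two endpoints fourth and fifth. That position is an inference.

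**Working it through.** The visible documents give no repeat-injection rate, event count or power for these endpoints, so there is no plan figure to reproduce.

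**1. Calendar.** Day = 7 × week + 1, so Week 4 = Day 29, Week 12 = Day 85 and Week 20 = Day 141. The repeat window is 141 − 29 = 112 days. By Day 85, 85 − 29 = 56 days have passed: 56/112 = 50%.

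**2. Does 20-week censoring change the Cox test?** The partial likelihood uses only the risk sets at event times. If all data are cut at Day 85, no event falls later, and a non-repeater is in the same risk sets whether labelled Day 85 or Day 141. One simulated trial for each hazard shape, fitted under both labels:
- constant hazard, 73 events: log HR −0.5269, SE 0.2407, p = 0.0286 under both;
- front-loaded hazard, 118 events: log HR −0.4611, SE 0.1875, p = 0.0139 under both.

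With a cut at the actual visit (assumed within 3 days of Day 85) or a calendar snapshot, the labels can differ by subject. A simulation at assumed 50% placebo repeat by Week 20, HR 0.65 and 52-week accrual moved the mean log HR by at most about 0.003 and changed significance in 0-2% of trials.

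**3. The Kaplan-Meier tail if the Week 12 cut covers injections.** Assumptions: placebo repeat probability p by Week 20 of 30-60%, no dropout, cumulative hazard H(t) = −ln(1 − p) × ((t − 4)/16)^k, with k = 1 (constant) or k = 0.5 (front-loaded). The flat curve reads 1 − exp(−H(12)) at Day 141 where the truth is p.

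| p | k = 0.5: read at Day 141 (error) | k = 1: read at Day 141 (error) |
|---|---|---|
| 30% | 22.3% (7.7 points) | 16.3% (13.7) |
| 40% | 30.3% (9.7) | 22.5% (17.5) |
| 50% | 38.7% (11.3) | 29.3% (20.7) |
| 60% | 47.7% (12.3) | 36.8% (23.2) |

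**4. The tail if the cut does not cover injections.** The read comes only after the last subject reaches Week 12. With uniform accrual over A weeks (assumed 52 to 104), the share with full 20-week follow-up is 1 − 8/A: 1 − 8/52 = 85% to 1 − 8/104 = 92%. Averaging the incidence over the follow-up of the rest (12 to 20 weeks), 97-99% of placebo Week 20 events are already seen. The Day 141 error is 0.3 to 1.7 points.

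**5. How far the Week 12 and Week 20 results could differ, if the cut applies.** Further assumptions: 200 per arm (about 400 randomized 1:1) and HR 0.6-0.7, proportional. Events d = 200 × {[1 − exp(−H)] + [1 − exp(−HR × H)]}; power = Φ(√(d/4) × |ln HR| − 1.96). At p = 50%, HR 0.6:
- k = 0.5: 128 events by Week 12 and 168 by Week 20; late share 23.6%; power 0.83 against 0.91;
- k = 1: 96 and 168; late share 42.8%; power 0.71 against 0.91.

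Over the whole grid, 22-26% (front-loaded) or 40-46% (constant) of events fall after Week 12. Treating the two test statistics as bivariate normal with correlation √(d12/d20), they disagree on significance in 7-19% or 16-31% of trials. If the cut does not apply, the two datasets are nearly the same (step 4) and these figures do not hold.

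**The case against.** The strongest reply is that SAP 7.1 already settles the matter. It reserves inference for the Week 12 read, describes the later additions as descriptive statistics, and cuts ongoing data at the Week 12 visit with an open list of examples that can include injection dates. With SAP 7.3.3 supplying the censoring time, Week 20 is then simply the end of the injection window. Blacked-out text in 7.1, or in the ordered list of 7.12.6.19, may say so outright.

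Most of this stands. A reader might infer that the Cox and chi-square tests have two competing confirmatory p-values, with an inflated error rate: if either read could be claimed at 5%, the type I error would be 6.5% to 8.6% for information fractions of 0.9 down to 0.4. The documents do not support that reading, because 7.1 names one inferential read. Nor do they show that a second p-value must appear. Producing the same outputs twice can mean the same tables with the Week 12 inference unchanged, and the output lists are redacted. A reader might also infer that the 20-week rule biases the hazard ratio; step 2 shows no effect, or a very small one.

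What the reply does not remove is the stated rule itself. SAP 7.12.6.2 specifically says 20 weeks, makes no exception for the Week 12 read, and differs from both 7.3.3 and the 7.1 cut. No visible sentence applies that cut to injection dates or gives the proportion a window.

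**Conclusion.** A real inconsistency, of minor weight. At the Week 12 read the censoring rule in SAP 7.12.6.2 overstates follow-up and conflicts with SAP 7.3.3, and the proportion in SAP 7.12.6.3 has no stated window.

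Its main visible effect is on one plot: about 8 to 23 points at Day 141 if the Week 12 cut covers injections, about 0 to 2 points if it does not. Both ranges rest on assumed repeat rates and hazard shapes, and the second also on assumed accrual. At the full analysis the 20-week rule fits the repeat window.

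The visible text already points to the Week 12 p-value as the confirmatory one, so labelling later results is a clarification. The primary and key secondary endpoints, both at Week 4, are untouched.

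**What to change.** Two changes of SAP wording; no study procedure changes.

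1. In SAP 7.12.6.2: *Subjects without a repeat injection will be censored at the earliest of discontinuation, the data cut-off of the analysis being reported, and Week 20.*
2. In SAP 7.12.6.2 and 7.12.6.3, state that the Week 12 cut-off in 7.1 applies to repeat-injection dates, so that both confirmatory tests use injections through the Week 12 visit (nominal Day 85), and that Week 20 results at the full analysis are descriptive. If redacted text already says this, cross-refer to it.

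The cost of the Week 12 horizon is fewer events in the confirmatory tests (about 22-46% fewer under the assumptions above) and no inference about Weeks 12 to 20. If Week 20 is what is meant, exempt both endpoints in 7.1 and say when their steps in the sequence are decided. Their p-values, and those of any endpoints behind them, would then come later. Injections given after the unblinding in Protocol 5.2.10 would also enter the tests. At the last Week 12 visit at most 8/104 to 8/52 of subjects, about 8-15%, would still be inside Weeks 12 to 20 under the accrual assumed above.

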Each subject will have the option of receiving 1 supplemental OL TF injection of SP-102 ("repeat injection"). To qualify for the repeat injection, subjects must meet Repeat Injection Inclusion Criteria, NPRS pain score in the affected leg, and investigator judgment, which includes a safety evaluation demonstrating no signs or symptoms of adrenal suppression or other safety concerns. The repeat injection may be administered between Weeks (W) 4 and 20. Eligible subjects will receive OL SP-102 repeat injection regardless of their initial treatment assignment (SP-102 or placebo).

In case of inadequate control of radicular pain, up to [REDACTED] will be allowed per day. The subject should be instructed to avoid use of acetaminophen within 6 hours prior to recording an NPRS score. Doses of rescue medication and time taken will be collected in the eDiaries until W12 and thereafter as a concomitant medication.

The subject will complete the eDiary twice daily approximately 12 hours apart (± 2 hours) to record their NPRS scores for pain in the previous 12 hours for 12 weeks following index injection. Thereafter, NPRS scores will be recorded at clinic visits.

All subjects will be seen at the clinic on D15, and every 4 weeks (ie, W4 [D29], W8 [D57], W12 [D85], W16 [D113], W20 [D141], and W24 [D169]) after the DB index injection for up to 24 weeks. Subjects receiving the OL repeat SP-102 injection will also be seen at the clinic 14 days after the repeat injection and continue the DB planned visits as well. The subject will also be contacted by telephone by the site staff 2 days after each IP injection to discuss their progress, any medications they are taking, and if they have had any adverse events (AEs).

The study visits and the planned efficacy analysis after all enrolled subjects have completed W12 are depicted in [Figure 3.1](#).

Figure 3.1: Study Schematic

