3.5.2.9 Clinic Visit (Week 16, Day 113)

On D113 ± 3 days, the subject should return to the site for a follow-up visit. The following

[REDACTED]

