In case of inadequate control of radicular pain, up to 3 g of acetaminophen as rescue medication will be allowed per day. The subject should be instructed to avoid use of acetaminophen in the 6

hours prior to recording an NPRS score. Doses of rescue medication and time taken will be collected in the eDiaries until Week 12 and thereafter as a concomitant medication.

The subject will complete the eDiary twice daily approximately 12 hours apart ( $\pm 2$  hours) to record their NPRS scores for pain in the previous 12 hours for 12 weeks following index injection. Thereafter, NPRS scores will be recorded at clinic visits.

All subjects will be seen at the clinic on Day 15, and every 4 weeks (ie, Week 4 [Day 29], Week 8 [Day 57], Week 12 [Day 85], Week 16 [Day 113], Week 20 [Day 141], and Week 24 [Day 169]) after the DB index injection for up to 24 weeks. Subjects receiving the OL repeat SP-102 injection will also be seen at the clinic 14 days after the repeat injection and continue the double-blind planned visits as well. Subjects will also be contacted by telephone by the site staff 2 days after each IPr injection to discuss their progress, any medications they are taking, and if they have had any adverse events (AEs).

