#### 7.3.3 Duration/Study Day/Time

Study day will be calculated as the number of days from first dose of SP-102 TF or placebo injection.

- date of event – date of first dose of SP-102 TF or placebo + 1, for events on or after first dose
- date of event – date of first dose of SP-102 TF or placebo, for events before first dose.

For all time to event analyses, subjects not reporting the specified endpoint will be censored at the time that the subjects were last known not to have experienced the endpoint. The last visit is a censoring event, and events that occur after the last visit will be disregarded in the statistical analysis. For all endpoints not encompassing death, all deaths will be treated as censoring events. In complex cases where the censoring time of the subject is uncertain, the case will be reviewed

by the Worldwide Clinical Trials (WCT) statistician and a censoring time will be assigned before database lock.

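### SAP 7.12.6.2 censors non-repeaters at Week 20 but sets no matching limit on repeat injections, so one repeat dated later forces that arm's Kaplan-Meier curve to zero

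*SAP*

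**What the plan says.** SAP 7.12.6.2 plans Kaplan-Meier quartiles with 95% confidence intervals, a survival plot and a Cox hazard ratio, SP-102 against placebo. Its general censoring rule is: "Subjects that do not receive a repeat injection will be censored at 20 weeks". Early leavers are handled separately, in these words: "subjects who discontinue the study prior to 20 weeks without receiving a repeat injection will be censored at the time of discontinuation". The section places no limit on event times.

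SAP 7.3.3 gives a different rule for every time-to-event analysis: "subjects not reporting the specified endpoint will be censored at the time that the subjects were last known not to have experienced the endpoint". It counts study days as "date of event – date of first dose of SP-102 TF or placebo + 1, for events on or after first dose". Neither section says whether 20 weeks means 140 elapsed days or study day 141, or which count the time to repeat uses.

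On timing, SAP 2 says "The repeat injection may be administered between Weeks 4 and 20". Protocol 3.1 lists the later visits as "W16 [D113], W20 [D141], and W24 [D169". For the Week 16 visit, Protocol 3.5.2.9 says "On D113 ± 3 days, the subject should return to the site for a follow-up visit"; Weeks 4 and 24 (Protocol 3.5.2.6 and 3.5.2.11) have the same ±3 days. The Week 20 text (Protocol 3.5.2.10) and the repeat-injection criteria (3.3.1.3) are redacted. SAP 7.3.8 allows repeat visits to be captured as unscheduled. Follow-up runs to Week 24.

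**The concern.** Events and censoring have different end points. Non-repeaters who stay in the study leave the risk set at 20 weeks, although they are still being observed. A subject whose repeat is dated later stays in and counts as an event. At that point the risk set holds only late repeaters, so the last of them takes the estimate to 0 whatever the true proportion repeating.

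At stake are the printed quartiles and the survival plot. A single subject out of about 200 could make the plot show everyone in an arm receiving a second injection by about Day 144.

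**Working it through.** The visible text gives no repeat rate, event count or expected quartile for this endpoint, and the sample-size sections are redacted. There is therefore no plan figure to reproduce.

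**Inputs.** About 400 randomized 1:1 (Protocol synopsis), so 400/2 = 200 per arm. Assumed: repeat proportions of 10% to 80%, dropout of 0% or 17% (17% being the loss implied by 332/400), and a Week 20 window of ±3 days, that is Day 138-144.

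**1. What 20 weeks means.** SAP 7.12.6.14, which is to be analyzed like this endpoint, censors the first 4 weeks at Day 29 and the first 12 weeks at Day 85. These are 4 × 7 + 1 = 29 and 12 × 7 + 1 = 85. By the same rule 20 × 7 + 1 = 141, the nominal Week 20 visit day.

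**2. The mechanism.** At each event time the estimate is multiplied by (1 − d/n), with d events among n at risk. Take 200 subjects, 40 repeats (20%) by the cut-off and no dropout, so S = 160/200 = 0.800. Add one repeat on day 143.
- Rule as written: n = 1, so S = 0.800 × (1 − 1/1) = 0.
- Non-repeaters at risk to last contact (168 elapsed days): n = 160, so S = 0.800 × (1 − 1/160) = 0.795.
- Everyone truncated at one common day: S stays at 0.800.

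**3. Quartiles.** A quartile is taken as the first time S(t) ≤ 1 − p. Q1, the median and Q3 are therefore false when S at the cut-off exceeds 0.75, 0.50 and 0.25 respectively. With one late repeat at day 143 and no dropout:

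| Repeating by cut-off | S at cut-off | Printed as 143, should be not reached |
|---|---|---|
| 10-20% | 0.90-0.80 | Q1, median, Q3 |
| 30-40% | 0.70-0.60 | median, Q3 |
| 50-70% | 0.50-0.30 | Q3 |
| 80% | 0.20 | none; only the tail of the curve |

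With 17% dropout the pattern is the same. These runs censored at day 140. Only the order of the late event and the censoring matters, and step 4 shows the same collapse with censoring at 141.

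**4. Day count** (20% repeating earlier, one further repeat).

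| Event day | Censoring day | Final S |
|---|---|---|
| 140 | 140 | 0.795 |
| 141 | 141 | 0.795 |
| 141 | 140 | 0 |
| 143 | 141 | 0 |

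On one common scale an on-time Week 20 repeat ties with the censoring and does no harm. A repeat on Day 142-144 collapses the curve under either reading of 20 weeks.

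**5. Cox model** (illustrative data, treatment only). Censoring at day 140 against last contact gives hazard ratios of 0.499 and 0.506 with one late repeat, and 0.509 and 0.493 with three in one arm and five in the other.

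**6. How likely is a late repeat?** Assume 112 subjects at risk in an arm at Week 20, a proportion p of them repeating at that visit, and a fraction f of those repeats dated after Day 141. Then P(at least one) = 1 − (1 − pf)^112. An even spread over Day 138-144 gives f = 3/7.
- p = 4%, f = 3/7: 86%
- p = 4%, f = 1/7: 47%
- p = 1%, f = 3/7: 38%
- p = 1%, f = 1/7: 15%

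**The case against.** The strongest defence is that 7.12.6.2 is a reasonable specific rule. The opportunity to repeat ends at Week 20, so censoring there is natural, and with 20 weeks read as Day 141 an on-time repeat is handled correctly. The redacted Week 20 and repeat-injection text may also rule out a repeat after Day 141. Much of this stands. A reader might infer that 20 weeks is 140 days while events carry the +1, so that even punctual Week 20 repeats break the curve. The documents do not support that: 7.12.6.14 points to Day 141, and nothing prescribes different scales for events and censoring.

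A reader might also infer that the collapse is close to certain. It is not. The visible text gives no repeat rates, and step 6 runs from 15% to 86% on assumed inputs.

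The defence does not remove the gap. If 7.12.6.2 is meant as an exception to 7.3.3, it does not say so, and an exception that ends the risk period at Week 20 needs the same end for events. SAP 7.3.3 does send uncertain censoring times to a statistician before database lock. Here, however, the censoring time is fixed by rule; what is missing is a limit on the events.

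**Conclusion.** The point holds as a gap in the censoring rule. The collapse follows from the estimator and needs no assumed rate, once a repeat is dated after the cut-off. That such a repeat will occur is an inference from the neighbouring ±3-day windows and the allowance for unscheduled repeat visits.

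The damage is limited to the survival plot and to quartiles not reached by the cut-off. It would be wrong to infer that all quartiles are false or that the treatment comparison is distorted: the hazard ratio changed by at most 0.016 (0.509 − 0.493) in the illustrative data, and the proportion receiving a repeat (SAP 7.12.6.3) is untouched. Early discontinuers are censored at discontinuation, so the 20-week rule does not cover every non-repeater, but this does not prevent the collapse.

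There is a related weakness. SAP 7.1 places the final inferential analysis after all subjects complete Week 12. Some may not yet have been observed to Week 20, and censoring them at 20 weeks would credit event-free time that nobody has observed.

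**What to change.** In SAP 7.12.6.2, state that event and censoring times both use the study-day count of 7.3.3, and reconcile the two sections in one of two ways:

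- **Follow 7.3.3.** Censor each non-repeater at the last day observed event-free, not at a 20-week point that may be unobserved.
- **Use one common cut-off day, named in days, for events and censoring.** A repeat dated after it is treated as event-free at the cut-off. Subjects who discontinue, or have not yet been observed to that day, are censored earlier, at their last observed day. State that this is an exception to 7.3.3.

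In the 20% example these give final values of 0.795 and 0.800, with all three quartiles correctly not reached. Moving only the censoring day to Day 144 would not be enough: it still departs from 7.3.3 for subjects followed to Week 24, and an unscheduled repeat after Day 144 would bring the collapse back.

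The cost is a sentence or two in the SAP and a small program change before unblinding. No new data are needed.
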